**Figure 1 - Tenofovir Blood Concentrations vs. Time after Vaginal Administration**

First letter = Cohort

Cohort A - HIV -uninfected/sexually abstinent

Cohort B - HIV -uninfected/sexually active

Cohort C - HIV-infected/sexually abstinent

Cohort D - HIV-infected/sexually active

4 digits = last 4 digits of participant identifier

Last digit = day of study

The current study will expand the ongoing evaluation of tenofovir gel into the term pregnant population. It is conceivable that the absorption and pharmacokinetics of tenofovir gel in the 3rd trimester of pregnancy may differ from the non-pregnant data above, given increased blood flow to the pelvic tissues and engorgement of the pelvic vessels. With hypothesized increased absorption from the pelvic tissues, the potential for placental transfer exists. This protocol will also evaluate that endpoint.

The validated LCMS (liquid chromatography mass spectrometry) method planned for MTN-002 has a limit of quantitation (LOQ) of 5 ng/mL, but uses only 50 microliters of fluid. Previous methods have had a LOQ of 3 ng/mL but used 250 microliters. Since assay sensitivity is largely determined by mass in the sample, not concentration, this likely represents a 3 fold improvement in sensitivity if we use a similar volume as in previous studies. To improve even further, we are planning to dedicate 1 mL serum for the blood tenofovir assay to further increase the sensitivity, possibly below 1 ng/mL. This may increase the number of samples quantifiable in the blood assuming similar pharmacokinetics as in HPTN 050.

No PK analysis is planned beyond description of  $C_{max}$  and  $T_{max}$ . Estimates of vaginal absorption, systemic clearance, volume of distribution, and half-life require accurate assessment of the initial rise in concentration, area under the concentration time curve (AUC), and terminal elimination slope. Since only the concentration at 1 – 3 time points near  $C_{max}$  in only some women (based on HPTN 050 experience) may be expected to be measurable, data from this study cannot be used to estimate initial absorption, AUC, or terminal elimination slope.

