### 4.2 Summary of Major Endpoints

- Maternal 3rd trimester pharmacokinetic measures (AUC, Cmax,)
- Endometrial tenofovir levels
- Placental transfer (cord blood tenofovir levels, placental tissue tenofovir levels, amniotic fluid tenofovir levels)

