### **7.9.2 Network Laboratory**

The Network Laboratory will run the following:

- Urine SDA for chlamydia and gonorrhea
- Trichomonas culture
- Pharmacokinetic analyses (at NL Pharmacology Core)

The following specimens will be collected for pharmacokinetic analyses of tenofovir according to guidelines outlined in the Site SOPs.

- Maternal blood
- Amniotic fluid
- Cord blood
- Placental tissue

- Endometrial tissue

Based on HPTN 050, 64% of measurable samples fell in the 2 to 6 hour sampling window which was the basis for selection of sampling times to maximize capture of peak levels in the blood. Measurable levels were spread almost evenly among the 2, 4, and 6 hour sample times. Subjects' peak tenofovir concentrations occurred throughout this window. In HPTN 050, 38% of measurable levels were after 4 hours so they are somewhat less likely to be measurable, but will be nearly as informative as the 4 hour sample.

MTN-002 will use a more sensitive tenofovir assay than HPTN 050. Our validated liquid chromatography mass spectrometry (LCMS) method has a limit of quantitation (LOQ) of 5 ng/mL, but uses only 50 microliters of fluid. Previous methods have had a LOQ of 3 ng/mL but used 250 microliters. Since assay sensitivity is largely determined by mass in the sample, not concentration, this likely represents a 3 fold improvement in sensitivity if we use a similar volume as in previous studies. To improve even further, we are planning to dedicate 1 mL serum for the blood tenofovir assay to further increase the sensitivity, possibly below 1 ng/mL. This may increase the number of samples quantifiable in the blood assuming similar pharmacokinetics as in HPTN 050.

As stated above, a validated assay for tenofovir in plasma is currently available. Validated assays for tenofovir in endometrial tissue, amniotic fluid and placental tissue have not yet been developed, but are expected to be ready in 2007. Pharmacokinetic samples may be batch shipped from the NL to the NL Pharmacology Core for assay.

The principal parameter of interest after intravaginal dosing will be the AUC. Plasma will also be analyzed for routine pharmacokinetic parameters ( $C_{max}$ ,  $T_{max}$ ).

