## **10.2 Study Major Endpoints**

Consistent with the primary and secondary study objectives, the following endpoints will be assessed:

- Maternal 3rd trimester pharmacokinetic measures: AUC, Cmax
- Endometrial tenofovir levels
- Placental transfer : cord blood tenofovir levels, placental tissue tenofovir levels, and amniotic fluid tenofovir levels

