### **10.6.2 Primary Analysis**

Descriptive statistics to assess women characteristics will be used: for categorical variables, the number and percent in each category; for continuous variables, the mean, median, standard deviation, quartiles and range (minimum, maximum). Similarly, descriptive statistics for continuous variables will be use to describe levels of tenofovir in levels in plasma, in endometrium, in cord blood, in placental tissue, and in amniotic fluid. If a substantial number of women are below the limit of detection of the assay, descriptive statistics for continuous variables will not be used. Rather, proportion of women with detectable levels will be computed along with an exact 95% confidence interval based on the Clopper-Pearson method.

Blood plasma pharmacokinetics of tenofovir will be evaluated after vaginal administration. Pharmacokinetic parameter estimates will include peak concentration ( $C_{max}$ ), time to peak concentration ( $T_{max}$ ), and area under the concentration time curve (AUC) for tenofovir in the blood. Descriptive statistics will be used to summarize these PK parameters in the cohort. Cord blood, amniotic fluid, placental tissue, and endometrial tissue tenofovir levels will also be summarized using descriptive statistics. The ratio of concentrations of tenofovir in maternal blood relative to temporally matched cord blood, amniotic fluid, and endometrial tissue concentrations, and ratio of maternal blood plasma relative to intracellular peripheral blood mononuclear cell (PBMC) tenofovir and tenofovir diphosphate levels will be calculated and summarized using descriptive statistics.

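### Section 7.9.2 makes AUC the principal parameter and other sections make it an endpoint and planned estimate, while section 2.10 says this study's data cannot be used to estimate it

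*Protocol*

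**What the plan says.** The primary objective (section 3.1) is maternal single-dose pharmacokinetics at term. The Protocol takes two positions on what that analysis contains.

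**AUC is planned.**
- Section 7.9.2: "The principal parameter of interest after intravaginal dosing will be the AUC". Cmax and Tmax come second: "Plasma will also be analyzed for routine pharmacokinetic parameters".
- Sections 4.2 and 10.2 list AUC, then Cmax, as the maternal PK major endpoints; in 10.2 the entry begins "trimester pharmacokinetic measures: AUC".
- Section 10.6.2 includes, with Cmax and Tmax, "area under the concentration time curve (AUC) for tenofovir in the blood" among the parameter estimates, to be summarised descriptively.

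**AUC is ruled out.**
- Section 2.10, in the text after Figure 1: "No PK analysis is planned beyond description of" Cmax and Tmax. Its closing sentence says that "data from this study cannot be used to estimate initial absorption, AUC, or terminal elimination slope". The reason given is that, from HPTN 050 experience, only one to three time points near Cmax may be measurable, and only in some women.

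Section 10.6.2 also has a fallback. If a substantial number of women are below the limit of detection, continuous summaries are replaced by the proportion detectable with a Clopper-Pearson interval. The fallback follows the sentence on tenofovir levels. AUC is introduced in the next paragraph, without that condition.

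**The concern.** An analysis plan cannot follow both 2.10 and 7.9.2. The conflict decides what the main result for the primary objective is: an exposure figure (AUC), or a description of peak level and time to peak.

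Left open, it allows two outcomes. The trial could report an AUC that its own rationale says the data cannot support. Or it could drop its stated principal parameter after the concentrations are known. In a 16-woman descriptive study, the second would look like a choice driven by results even if it were sensible.

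Section 2.10's reason is also substantive. If most women have no measurable level, an AUC computed across the cohort largely reflects a convention for values below the limit of quantitation (BLQ).

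**Working it through.** The contradiction is textual, and the Protocol states no AUC figure to reproduce. The arithmetic below only shows why section 2.10's reason matters.

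**1. Could other text reconcile the sections?**
- *Assay sensitivity.* Section 2.10 describes the hoped-for gain from a 1 mL sample, possibly below 1 ng/mL, and in its next paragraph still concludes that AUC cannot be estimated. Section 7.9.2 repeats the assay text and then names AUC principal. The same assay information precedes opposite conclusions.
- *The 10.6.2 fallback.* It is worded for tenofovir levels and does not say that AUC is dropped.
- *Sample size.* Section 10.4 rests on proportions with detectable drug, so it does not settle the status of AUC.

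**2. How many women would have no measurable plasma level?**
Inputs: n = 16 (section 10.4); hypothesised plasma detection of about 33% (section 10.3).
16 × (1 − 0.33) = 10.7, about 11 women.
Section 2.10 also reports 14 of 25 (56%) detectable on at least one of two dosing days in HPTN 050. At 56% the count would be 16 × 0.44 = 7.0.

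**3. What AUC(0-24) would such a woman be given?**
Inputs: post-dose samples at 1, 2, 4, 6, 8, 12 and 24 h (section 4.1). Assumptions, not in the Protocol: linear trapezoid, pre-dose value 0, and every BLQ value replaced by a constant c.
- First interval: (0 + c)/2 × 1 = 0.5c.
- 1 to 24 h: 23c.
- Total: 23.5c.

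| Limit (ng/mL) | Source | c = 0 | c = half the limit |
|---|---|---|---|
| 1 | Upper end of the hoped-for 1 mL performance | 0 | 23.5 × 0.5 = 11.75 |
| 3 | HPTN 050 assay | 0 | 23.5 × 1.5 = 35.25 |
| 5 | Validated method at 50 microliters | 0 | 23.5 × 2.5 = 58.75 |

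**4. How does that compare with a measurable signal?**
Take one measurable value of 3.4 ng/mL (the HPTN 050 median Cmax, section 2.10), placed by assumption at 4 h.
- c = 0: (0 + 3.4)/2 × 2 + (3.4 + 0)/2 × 2 = 6.8 ng·h/mL.
- c > 0: 23.5c + 2 × (3.4 − c).
- Limit 3: 35.25 + 3.8 = 39.05. The rule moves AUC by 39.05 − 6.8 = 32.25, or 4.7 times 6.8.
- Limit 1: 11.75 + 5.8 = 17.55. The rule moves AUC by 17.55 − 6.8 = 10.75, or 1.6 times 6.8.
- Limit 5: 3.4 is itself below the limit.

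At each limit where the comparison can be made, the substitution rule moves AUC by more than the single measurable value contributes. The ratio depends on the assumed limit.

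**The case against.** Several counter-arguments have force.

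**The fallback limits the damage.** With about 11 of 16 women below the limit, 10.6.2 would replace continuous summaries of levels by a proportion detectable. A reader might infer that the plan commits the trial to a misleading headline AUC. The documents do not support that: the fallback shows awareness of the problem, and hypothesis 1 and section 10.4 already rest on detection. What remains is that the fallback never reaches AUC and 7.9.2 still calls AUC principal.

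**The size is assumption-dependent.** A reader might infer from the 3 ng/mL row that the substitution rule outweighs the drug signal about fivefold. That is not established. The 3 ng/mL limit belongs to HPTN 050, the Protocol prescribes no half-limit rule, and at 1 ng/mL the ratio is 1.6. A more sensitive assay might also raise the detection rate. Handling of BLQ values may properly sit in the statistical analysis plan, so its absence here is not the fault.

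**The dissenting text is in the Introduction.** Four design or analysis sections name AUC, and sampling to 24 h is compatible with it. The conflict could therefore be resolved in favour of AUC. That is fair, and it argues for offering both routes. It does not remove the contradiction.

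**Cmax shares the weakness.** If about 11 women have no measurable level, their Cmax is also below the limit, and so is the cohort median. Replacing AUC by Cmax alone would not solve the problem. This stands and shapes the fix.

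**Nothing formal rests on AUC.** The study is single-arm and descriptive, and no test, power figure or stopping decision uses AUC. True, but AUC is still the named principal parameter for the only primary objective.

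**Conclusion.** The contradiction is real and wrong as written. Section 2.10 rules out AUC; section 7.9.2 makes it principal, 4.2 and 10.2 make it a major endpoint, and 10.6.2 plans to estimate it. Only 7.9.2 uses the word principal; the other sections list AUC beside Cmax (and Tmax in 10.6.2). This conclusion rests on the text alone.

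The consequence is less certain in size. If plasma detection is about 33%, roughly 11 of 16 women would have an AUC set by the BLQ convention: zero, or about 12 to 59 ng·h/mL under half-limit substitution at limits of 1 to 5 ng/mL. Those values are illustrative. They assume a linear trapezoid, a zero pre-dose level and a substitution rule that the Protocol does not state.

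**What to change.** Reconcile the sections before any concentration data are seen.

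**Default: bring 4.2, 7.9.2, 10.2 and 10.6.2 into line with 2.10.**
- Lead with the proportion of women with detectable plasma tenofovir and its exact confidence interval. Hypothesis 1 already targets this, and it is the measure closest to section 10.4, whose overall rate also counts detection in other specimens.
- Report Cmax and Tmax descriptively, with BLQ values shown as below the limit, using median and range.
- Extend the 10.6.2 fallback explicitly to AUC and Cmax. Any AUC is then exploratory, with the number of contributing women shown. Restricting AUC to women with at least three quantifiable values would not be a sound substitute: the Protocol gives no such threshold, it selects the higher absorbers, and with one to three measurable points expected the subset could be nearly empty.

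**Alternative: keep AUC.** If the achieved 1 mL assay limit supports it, revise 2.10 and state the interval, the minimum number of quantifiable points and the BLQ rule under which AUC is computed.

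**Cost.** The change is wording, but as an amendment it needs the approvals in section 13.2, including the IRB and the RCC. Under the default, AUC may cease to be a headline parameter. No stated sample size or power figure changes under either route.

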### **7.10 Specimen Collection and Processing**

Each study site will adhere to the standards of good clinical laboratory practice, the HPTN-MTN Network Laboratory Manual, DAIDS Laboratory Requirements, and site standard operating procedures for proper collection, processing, labeling, transport, and storage of specimens at the local laboratory. Specimen collection, testing, and storage will be documented when applicable using the Laboratory Data Management System (LDMS). In cases where laboratory results are not available due to administrative or laboratory error, sites are permitted to re-draw specimens as outlined in the site SOPs.

### **7.11 Specimen Handling**

Specimens will be handled in accordance with Requirements for DAIDS Sponsored and/or Funded Laboratories in Clinical Trials.

## **7.12 Biohazard Containment**

As the transmission of HIV and other blood-borne pathogens can occur through contact with contaminated needles, blood, and blood products, appropriate blood and secretion precautions will be employed by all personnel in the drawing of blood and shipping and handling of all specimens for this study. All dangerous goods materials, including diagnostic specimens and infectious substances, must be transported according to instructions detailed in the International Air Transport Association (IATA) Dangerous Goods Regulations. Biohazardous waste will be contained according to institutional, transportation/carrier, and all other applicable regulations.

# **8 ASSESSMENT OF SAFETY**

## **8.1 Safety Monitoring**

The study site investigators are responsible for continuous close safety monitoring of all study participants, and for alerting the Protocol Team if unexpected concerns arise. A sub-group of the Protocol Team, including the Protocol Chair or designee, Medical Officers, SDMC Clinical Affairs Research Nurse, and Protocol Statistician, will serve as the PSRT. The PSRT will be co-chaired by the protocol safety physicians in the MTN CORE. Close cooperation among the PSRT and other study team members will be necessary to monitor participant safety and respond to occurrences of toxicity in a timely manner. The MTN SDMC prepares routine AE and clinical data reports for review by the PSRT, which meets via conference call approximately every month or as needed throughout the period of study implementation to review safety data, discuss product use management and address any potential safety concerns.

## **8.2 Clinical Data Safety Review**

A multi-tiered safety review process will be followed for the duration of this study. The study site investigators are responsible for the initial evaluation and reporting of safety information at the participant level, and for alerting the PSRT if unexpected concerns arise. Participant safety is also monitored at the Network level through a series of routine reviews conducted by the SDMC Clinical Affairs staff, the PSRT and study sponsors. Additional reviews may be conducted at each of these levels as dictated by the occurrence of certain events.

MTN SDMC Clinical Affairs staff will review incoming safety data on an ongoing basis. Events identified as questionable, inconsistent, or unexplained will be queried for verification. Adverse event reports submitted in an expedited manner to the DAIDS Safety Office will be forwarded to the NICHD and DAIDS Medical Officers and SDMC Clinical Affairs staff for review.

The PSRT will meet approximately every month via conference call to review clinical data reports generated by the MTN SDMC. The content, format and frequency of the clinical data reports will be agreed upon by the PSRT and the SDMC in advance of study implementation. In addition to the routine safety data reviews, the PSRT will convene on an ad hoc basis to make decisions regarding the handling of any significant safety concerns. If necessary, experts external to the MTN representing expertise in the fields of microbicides, biostatistics, HIV transmission and medical ethics may be invited to join the PSRT safety review. A decision to stop the trial may be made by the PSRT at this time or at any such time that the team agrees that an unacceptable type and/or frequency of AEs has been observed.

In the unlikely event that the protocol team has serious safety concerns that lead to a decision to permanently stop accrual into the study, the protocol team will request a review of the data by the Study Monitoring Committee (SMC) before deciding that the study be stopped. Members of the SMC will be independent investigators with no financial interest in the outcomes of this study. If at any time a decision is made to discontinue enrollment, DAIDS will notify the US FDA and the site CRS PI will notify the responsible IRB expeditiously.

### **8.3 Adverse Events Definitions and Reporting Requirements**

#### **8.3.1 Adverse Events**

An AE is defined as any untoward medical occurrence in a clinical research participant administered an investigational product and which does not necessarily have a causal relationship with the investigational product. As such, an AE can be an unfavorable or unintended sign (including an abnormal laboratory finding, for example), symptom or disease temporally associated with the use of an investigational product, whether or not considered related to the product. The term “investigational product” for this study refers to tenofovir gel.

Study participants will be instructed to contact the study site staff to report any AEs they may experience, except for life-threatening events, for which they will be instructed to seek immediate emergency care. Where feasible and medically appropriate, participants will be encouraged to seek medical care where the study clinician is based, and to request that the clinician be contacted upon their arrival. With appropriate permission of the participant, and whenever possible, records from all non-study medical providers related to AEs will be obtained and required data elements will be recorded on study case report forms. All participants reporting an AE (including pelvic exam abnormalities) will be followed clinically until the AE resolves (returns to baseline) or stabilizes.

Study site staff will document on study CRFs all AEs reported by or observed in enrolled study participants from the time of enrollment until study termination, regardless of severity and presumed relationship to study product. The Protocol Specific Toxicity

Table (Appendix V) will be the primary tool for grading adverse events for this protocol, with the exception of asymptomatic bacterial vaginosis which will not be a reportable AE. Adverse events not included in that table will be graded by the DAIDS AE Grading Table Version 1.0, December 2004. In cases where an AE is covered in both tables, the Protocol Specific Toxicity Table will be the grading scale utilized.

### **8.3.2 Serious Adverse Event**

Serious adverse events (SAEs) will be defined per 21 CFR 312.32 guidelines as AEs occurring at any dose that:

- Result in death
- Are life-threatening adverse events
- Require Inpatient hospitalization or prolongation of existing hospitalization
- Result in persistent or significant disability/incapacity, or
- Are congenital anomalies/birth defects

Important medical events that may not result in death, be life-threatening, or require hospitalization may be considered serious when, based upon appropriate medical judgment, they may jeopardize the participant or require medical or surgical intervention to prevent one of the outcomes listed above.

### **8.3.3 Adverse Event Relationship to Study Product**

Relatedness is an assessment made by a study clinician of whether or not the event is related to the study agent. Degrees of relatedness will be categorized as one of the following.

- *Definitely related:* adverse event and administration of study agent are related in time, and a direct association can be demonstrated with the study agent.
- *Probably related:* adverse event and administration of study agent are reasonably related in time, and the adverse event is more likely explained by the study agent than by other causes.
- *Possibly related:* adverse event and administration of study agent are reasonably related in time, and the adverse event can be explained equally well by causes other than the study agent.
- *Probably not related:* a potential relationship between administration of study agent and adverse event could exist, but is unlikely, and the adverse event is most likely explained by causes other than the study agent.

- *Not related*: the adverse event is clearly explained by another cause unrelated to administration of the study agent. Reportable events must have documentation to support the determination of “not related”.

